4 STUDY DESIGN

This is a prospective, single arm, phase I/II trial to evaluate the safety and efficacy of fetal embolization for patients with vein of Galen malformations. The trial uses a Simon's optimal two-stage design for both the primary safety and secondary efficacy endpoints. More details can be found in the Statistical Considerations section.

Up to 25 subjects will be enrolled in this trial to obtain a cohort of 20 evaluable subjects. The MFCC is an international referral center for management of VOGM. In 2018, 40 neonatal VOGM embolizations were performed, and 30 in 2017. We expect recruitment to take place over 5-7 years. Study participation will extend from the time of consent through approximately 2 years post-birth (adjusted for gestational age) and data analysis will take place for approximately one year after the last subject has completed the study.

5 STUDY ENROLLMENT AND WITHDRAWAL

The intention of the Inclusion/Exclusion Criteria is to ensure evaluation of the safety of fetal embolization of vein of Galen malformation ONLY in fetuses in whom rescue is plausible, NOT in all fetuses in whom the procedure could be performed from a technical standpoint.

The study population will be delineated using the judgment of the principal investigators and an eligibility committee (see below) regarding whether or not (i) the fetus has already sustained irreversible major brain or other organ injury (SFP cohort) and (ii) the vein of Galen malformation has imaging characteristics such that the patient is likely to fall into the IT category and thus has a more favorable prognosis. Because the protocol offers a novel treatment approach with a potential for direct harm to individual fetuses and their mothers, only fetuses with the highest chance of deriving benefit from the procedure will be enrolled (i.e. the NAR cohort and neither the IT nor the SFP cohorts).

An eligibility committee will be consulted to review eligibility for each potential subject. The committee will consist of the principal investigators, Drs. [name] and [name], as well as [name], a neuroradiologist at BCH, and [name], an experienced senior pediatric developmental neurologist, who consults regularly on neurological prognosis at the MFCC. Subjects will only be enrolled if all committee members determine that the eligibility criteria are met.

5.1 Subject Inclusion Criteria

In order to be eligible to participate in this study, an individual must meet all of the following criteria:

1. *Pregnant woman carrying a fetus harboring a vein of Galen malformation in whom the straight sinus or falcine sinus draining the prosencephalic varix measures 7 mm or more on fetal MRI (medio-lateral diameter measured at the narrowest point of the sinus along the rostral-caudal axis, assessed on a T2-weighted coronal slice).*
2. *Fetal gestational age between 23 weeks and term as determined by clinical information and evaluation of first ultrasound.* Although it is believed that the VOGM forms between gestational weeks 6-11 (the developmental window during which the prosencephalic vein of Markowski is present before involution [17]), diagnosis of the condition by fetal ultrasound has never been reported prior to 22 weeks, likely because of the small size of the varix prior to that point. In principle, embolization of the malformation at any time after identification and prior to delivery could forestall the development of brain, cardiopulmonary, and other organ injury. The presence of the low-pressure placental circulation and the fetal lower-flow baseline cerebral circulation might be protective, in terms of reducing potential morbidity from intracranial hemodynamic shifts that accompany embolization. The suitability for fetal treatment, in terms of technical/positional factors, will be assessed on a case-by-case basis by the MFM, ultrasonographer, and neurointerventionalist participating in the study.
3. *Anatomic diagnosis of fetal vein of Galen malformation.* Various cerebrovascular conditions, such as dural sinus malformation and pial arteriovenous fistula, can result in dilated intracranial vascular structures being visualized in utero. Similarly, fetal dilatation

of the vein of Galen can occasionally be seen without the presence of an arteriovenous lesion at all, as a benign venous variant. This condition is readily distinguishable sonographically from VOGM by virtue of the presence of dilated arterial feeding pedicles, and by the presence of an arterial waveform within the varix. This study is aimed solely at fetuses with an established diagnosis of vein of Galen malformation.

4. *Well preserved brain parenchyma.* In some cases, significant bihemispheric cerebral parenchymal injuries with gliosis are seen at the time of initial fetal diagnosis of vein of Galen malformation (SFP cohort). Such fetuses rarely survive, but if they do, are profoundly neurodevelopmentally impaired: typically blind, mute, quadriparetic, often with unremitting intractable seizures, and permanently bedbound and uncommunicative. As there is no realistic possibility of achieving a good neurological outcome in such patients, fetuses with diffuse bihemispheric brain injury will not be candidates for inclusion. On the other hand, the presence of small and focal brain parenchymal injury on fetal MR (parameters defined below) in a fetus with vein of Galen malformation would not be an exclusion criterion. Given the overall intactness of the brain parenchyma in such fetuses at the time of diagnosis, it is reasonable to expect that treatment of the underlying VOGM in utero might preclude further brain injury.
5. *Maternal age of 18 years and older*
6. *Eligible for continuous lumbar epidural anesthesia*
7. *Able to travel to study site for study evaluation, procedures and visits*

5.2 Subject Exclusion Criteria

An individual who meets any of the following criteria will be excluded from participation in this study:

1. *Extensive fetal brain parenchymal injury/gliosis, >10% of supratentorial brain volume (i.e., SFP presentation). This is a degree of fetal brain injury beyond which the risk of significant neurological morbidity is high, based on studies of prenatal ischemic stroke [18-22].*
2. *Irreversible fetal non-brain organ injury (e.g. hydrops fetalis as a manifestation of heart failure, a finding which portends fatal outcome in fetuses with vein of Galen malformation), i.e., SFP presentation.*
3. *Fetus with VOGM in whom the straight sinus or falcine sinus draining the prosencephalic varix measures less than 7 mm on fetal MRI (T2-weighted coronal slice, medio-lateral diameter measured at the narrowest point of the sinus along the anterior-posterior axis), fitting fetal MRI criteria for likely evolution into the IT cohort*
4. *Severe maternal obesity pre-pregnancy as defined by body mass index (BMI) of 40 or greater*
5. *Fetuses with major congenital anomalies*

6. *Evidence of preterm labor, rupture of membranes or abruption*
7. *Maternal coagulopathy: INR > 1.2; PT/PTT above normal ranges for the lab; platelets <100*
8. *Medical disease requiring current anticoagulation including maternal deep vein thrombosis*
9. *Prior maternal medical history that would preclude epidural anesthesia*
10. *Multi-fetal pregnancy*
11. *Placenta previa or accreta*
12. *Participation in another fetal study that influences maternal and fetal morbidity and mortality*
13. *Known maternal hypersensitivity to 316LM stainless steel*
14. *Supine hypotensive syndrome*

5.3 Strategies for Recruitment and Retention

Participation in the study will be offered to patients who seek clinical consultation at the MFCC once fetal diagnosis of VOGM has been made. Additionally, the study will be described on VOGM online family support group sites and at national Maternal Fetal Medicine meetings and forums. A letter will also be sent out to physicians at outside institutions who see high-risk obstetric patients informing them of the study.

In accordance with federal regulations, no inducements, monetary or otherwise, will be offered to terminate a pregnancy; individuals engaged in the research will have no part in any decisions as to the timing, method, or procedures used to terminate a pregnancy; and individuals engaged in the research will have no part in determining the viability of a neonate.

5.4 Subject Withdrawal

5.4.1 Reasons for Withdrawal

Subjects are free to withdraw from participation in the study at any time upon request.

An investigator may terminate a study subject's participation in the study if:

- Any clinical adverse event (AE), laboratory abnormality, or other medical condition or situation occurs such that continued participation in the study would not be in the best interest of the subject.
- The subject meets an exclusion criterion (either newly developed or not previously recognized) that precludes further study participation.

- Ideal fetal positioning for the procedure cannot be achieved over a duration of 40 minutes with epidural analgesia; a single, separate 40 minute attempt may be undertaken at > 24hrs after the first attempt.
- The fetal embolization procedure is attempted but unable to be completed for any reason.

5.4.2 *Handling of Subject Withdrawals*

Any subject withdrawn prior to completing the fetal embolization will be replaced. The enrollment goal of the study is to achieve a cohort of 20 evaluable participants who have completed the intervention.

All subjects enrolled in the study will plan to deliver at BWH. In the event that there is an unplanned delivery at an institution other than BWH, the subject will receive standard of care at the outside institution. We will be available for consultation and, as is the case for non-research subjects, would consider the benefits and risks of transfer to BCH versus local treatment, depending on the clinical severity of the neonate. All advice will be purely based on the best medical interest of the baby, and not the research study. We will attempt to collect all relevant clinical information from the outside institution.

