11.2 Sample Size Considerations

We estimate, based on published results and our own experience, that 65% of all neonates born with vein of Galen malformation require urgent neonatal intervention (i.e. are NAR), under current standard of care. Thus, in order to achieve a cohort size of 20 treated patients, we expect to consent and screen 28-30 fetal patients. We expect to enroll 25 participants to account for withdrawals prior to completing the intervention (due to failure to achieve near ideal fetal position or other reasons). The study will be closed to enrollment once 20 participants have completed the intervention. Using the prescreening technique we have developed based on fetal MRI measurement of straight sinus or falcine sinus caliber at the narrowest point, we can estimate that 80% of all such fetal VOGM patients will progress to NAR status without fetal intervention. Setting a goal of reducing this fraction to 30% NAR status after fetal intervention (i.e., a 50% absolute reduction), the proposed sample size will provide 80% power to detect a significant effect of fetal intervention.

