11.3 Safety Review

Two-stage design for safety endpoint

In Stage 1, up to 11 evaluable patients will be enrolled (**Table 2**). Out of 11 patients, if 3 or more patients experience an unacceptable event (see definition in Section 3.2 above and recapitulated below Table 2), the intervention is unsafe and not worthy of further study. If 2 or fewer experience any unacceptable event, the trial will proceed to Stage 2, where an additional 9 evaluable patients will be enrolled, for a total of $N=20$ evaluable patients. Out of $N=20$ patients, if 4 or more patients experience any unacceptable event, the intervention is unsafe and not worthy of further study. If 3 or fewer patients experience any unacceptable event, the intervention is sufficiently safe and worthy of further study. In addition, in case of a single maternal death, the study will be halted pending review by the DSMB and the FDA.

This design tests the null hypothesis that the rate of unacceptable events is $P > 30\%$ versus the alternative that $P < 5\%$. The total type I error rate is 0.097 and the power is 97.5%. If the intervention is truly unsafe, there is a 68.7% probability of early trial termination.

Table 2: Decision rules for safety based on the optimum two-stage design.

	Cumulative number of patients with unacceptable events	Decision
Stage 1: Enroll 11 patients	3 or more	Terminate the trial: agent not worthy of further study
	2 or fewer	Inconclusive result: proceed to Stage 2
Stage 2: Enroll 9 additional patients	4 or more	Terminate the trial: agent not worthy of further study
	3 or fewer	Trial concludes: agent worthy of further study

- 1) Unacceptable events within 7 days of fetal embolization include:
 - a) Fetal death
 - b) Fetal intracranial hemorrhage, either parenchymal or extra-axial, other than petechial hemorrhage. A petechial hemorrhage is seen as focal staining of the brain parenchyma by blood products on MRI, is not associated with mass effect, and there are minimal neurologic sequelae. Petechial hemorrhages are usually considered non-serious adverse events in trials.
 - c) Maternal death
- 2) Unacceptable events occur between fetal embolization and delivery include:
 - a) Intra-procedural and post-procedural morbidity to the fetus and mother, probably related to the fetal intervention, e.g. placental abruption with subsequent sequelae
 - b) Preterm delivery < 28 weeks, probably related to the fetal intervention

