11.5 Timing of safety and efficacy rules

The safety endpoint is observed from Day 0 (the day of fetal intervention) to Day 7 post-intervention. The efficacy endpoint is observed from the birth to Day 30 of life. Both safety and efficacy decision rules must be satisfied before enrollment to Stage 2 is allowed. Prior to initiating accrual at Stage 2, a sensitivity analysis will be performed to determine if both the safety and efficacy rules would be triggered. Hence, trial enrollment for Stage 2 may be suspended after the enrollment of the 11th patient to allow observation up to Day 30 of life of the most recently treated patient.

The safety and efficacy rules are to be interpreted as specifying that the trial will stop as soon as either criterion is reached; e.g., if the first 3 evaluable patients experience unacceptable prenatal events (safety rule), or the first 6 patients experience serious postnatal events (efficacy rule), then the trial stops immediately. Beyond the 11th patient, the trial halts as soon as 4 unacceptable prenatal events or 10 serious postnatal events occur.

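### The plan never defines *evaluable* for safety, so its withdrawal and replacement rules can be read to leave an unacceptable event that aborts an embolization out of the 3-of-11 and 4-of-20 safety count

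*Combined protocol and SAP*

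**What the plan says.** Section 5.4.1 lists circumstances in which the investigator may end a subject's participation. One is: "The fetal embolization procedure is attempted but unable to be completed for any reason". Section 5.4.2 then says "Any subject withdrawn prior to completing the fetal embolization will be replaced" and adds "The enrollment goal of the study is to achieve a cohort of 20 evaluable participants who have completed the intervention". Section 4 allows five spare places: "Up to 25 subjects will be enrolled in this trial to obtain a cohort of 20 evaluable subjects". Section 11.2 closes the trial on completers: "The study will be closed to enrollment once 20 participants have completed the intervention".

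Section 11.3 sets the safety rule. "In Stage 1, up to 11 evaluable patients will be enrolled"; three or more with an unacceptable event stops the trial. Nine more follow, and four or more of 20 evaluable patients means unsafe. The stated type I error is 0.097, power 97.5% and early termination 68.7%.

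Section 3.2, repeated in 11.3, lists the unacceptable events. Fetal death, non-petechial hemorrhage and intra-procedural morbidity are among them, and none is conditional on the embolization having been completed. Part 1 of the endpoint covers seven days; part 2 runs to delivery.

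**The concern.** The primary objective is prenatal safety, and a complication during needle passage, navigation or coil deployment is an obvious reason to abandon the procedure. The nearest the protocol comes to saying who is evaluable is 5.4.2, which ties the word to completion. If the term carries that meaning into 11.3, a subject whose procedure was abandoned because of a hemorrhage or fetal death is withdrawn and replaced, and appears in neither the numerator nor the denominator.

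The limits are small, so one event counted or not counted can change the decision. Withdrawal is also discretionary and can be decided after the event is known. It ends participation, so new part 2 events between the aborted procedure and delivery may not be observed.

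**Working it through.** **Reproducing the stated design.** Inputs from 11.1 and 11.3: null risk 0.30, alternative 0.05, stop at 3 or more of 11, unsafe at 4 or more of 20.

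P(safe | p) = Σ over x = 0, 1, 2 of P(Bin(11, p) = x) × P(Bin(9, p) ≤ 3 − x)

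At p = 0.30:

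- x = 0: 0.01977 × 0.72966 = 0.0144
- x = 1: 0.09322 × 0.46283 = 0.0431
- x = 2: 0.19975 × 0.19600 = 0.0392
- Sum: 0.0967 (stated 0.097)
- Early stop: 1 − (0.01977 + 0.09322 + 0.19975) = 0.6873 (stated 68.7%)

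At p = 0.05, P(safe) = 0.9755 (stated 97.5%). The plan's arithmetic is right for whatever population is counted.

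**Effect of leaving aborted cases out.** Assume a true risk of 30% per attempt. Let a be the proportion of attempts with an event and aborted, and b the proportion event-free and aborted. Neither is in the documents. If both groups are replaced and uncounted, the event risk among completers is

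q = (0.30 − a) / (1 − a − b)

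and q replaces p above. For example, a = 0.05, b = 0 gives q = 0.25/0.95 = 0.2632 and P(safe) = 0.171. P(declared safe), with no enrollment cap:

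| b (points) | a = 2 | a = 5 | a = 10 | a = 15 |
|---|---|---|---|---|
| 0 | 12.2% | 17.1% | 29.5% | 48.6% |
| 5 | 9.5% | 13.8% | 25.0% | 43.6% |
| 10 | 7.1% | 10.6% | 20.6% | 38.2% |
| 15 | 5.0% | 7.8% | 16.2% | 32.5% |

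Four of the 16 cells lie below 9.7%. The bias is towards safe when q < 0.30, that is, when 0.3b < 0.7a. The break-even b = 0.7a/0.3 is 4.7, 11.7, 23.3 and 35.0 points for a = 2, 5, 10 and 15. Note that a = 5 means one unacceptable event in six aborts the procedure (5/30), and a = 15 means half do.

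**Effect of the 25-subject cap, kept separate.** The documents do not say how a trial is judged if it enrolls 25 without reaching 20 completers. If it is treated as not declared safe, an exact recursion over enrollees gives 12.2%, 17.1%, 28.5% and 40.7% at b = 0, and 3.8%, 4.8%, 6.1% and 6.3% at b = 15. At a = b = 15, 20 completers need 20/(1 − 0.30) = 28.6 enrollees on average and 35.5% of trials end undecided. The fall from 32.5% to 6.3% there comes from the cap assumption, not from the counting rule.

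**A possible path.** Five subjects aborted with events, plus three events among 20 completers with at most two in the first 11, is 8/25 = 32%, above the null rate. Counted over completers it is 3/20 = 15%, and the conclusion is sufficiently safe.

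**Counting the events but still replacing the subjects (b = 0).** At 30% risk, P(declared safe) is 9.3%, 8.7%, 7.7% and 6.9% for a = 2, 5, 10 and 15. At 5% risk, with the same shares of events aborting, it is 97.4% to 96.7%.

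**The case against.** The exclusion is an inference. No sentence says that these events are discarded. Section 5.4.2 states an enrollment goal, and if evaluable already meant completed, its last clause would be redundant. In ordinary usage a subject with an observed unacceptable event is evaluable for safety. Replacement fills a place; it does not erase an event. It applies only to subjects actually withdrawn, and the one example in 11.2 is failure to position the fetus. All of this stands, and it is why the defect is an unsettled rule and not a stated exclusion.

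Oversight is also substantial. Events are recorded from the start of the procedure and followed to resolution or stabilization (8.2). Every serious adverse event goes to the DSMB, which judges whether stoppage criteria are met (9). A maternal death halts the study (8.5, 11.3), and 5.5 permits termination for unacceptable risk. So a reader should not infer that such harm would go unseen. But none of these provisions says whether the event enters the 3-of-11 or 4-of-20 count, and the DSMB charter is not among the documents.

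A reader might also see a flat contradiction with 7.4 and the end of 11.5. The documents support less. Section 7.4 keeps a subject in the safety calculation after termination of pregnancy for major cerebral injury, not after an aborted procedure, so it is at most indirect. Section 11.5 uses *evaluable* in one clause and drops it in the next, which looks like loose wording.

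**Conclusion.** The concern holds as an ambiguity in the primary safety count that should be fixed. Confidence is medium, because it rests on combining 5.4, 11.2 and 11.3 around an undefined term. The stated error rates are correct arithmetic, but they describe risk per attempted procedure only if aborted cases are counted.

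On the excluding reading, at 30% true risk and 2 to 5 points of event-aborted attempts, the chance of a safe verdict is 12.2% to 17.1% with no event-free aborts and 9.5% to 13.8% with 5 points of them, against 9.7%. The larger figures need a third to a half of all unacceptable events to abort the procedure. Half is an upper extreme, since preterm delivery, imaging injury and later fetal death usually arise after completion.

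Two stronger readings are not supported: that the bias always favours safety, since it reverses once b exceeds 0.7a/0.3; and that it reverses easily, since much of that impression comes from an assumption about the cap.

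**What to change.** Reconcile 5.4.2, 11.2, 11.3 and 11.5 by adding to 11.3 and 11.5: *An unacceptable event in any subject in whom the invasive part of the procedure was begun counts toward the safety limits, whether or not the embolization was completed or the subject was withdrawn or replaced.*

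Define safety-evaluable to match, naming one start point after positioning. State that these subjects stay in safety data collection to delivery, so that part 2 of the endpoint is observed. Completers can remain the basis for replacement, technical success and efficacy. State how a trial is judged that reaches 25 enrolled without 20 completers.

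The cost is some redrafting, follow-up of a few subjects, restated operating characteristics, and the slightly stricter rule shown in the working.

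Counting every start toward the 11 and the 20 is optional. If it is adopted, the protocol must also say how the safety and efficacy Stage 1 looks align when starts pass 11 before there are 11 completers, because 11.5 requires both rules to be met before Stage 2.

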5.5 Premature Termination or Suspension of Study

This study may be suspended or prematurely terminated if there is sufficient reasonable cause. Written notification, documenting the reason for study suspension or termination, will be provided by the suspending or terminating party to investigator, Investigational Device Exemption (IDE) sponsor and regulatory authorities. If the study is prematurely terminated or suspended, the principal investigator will promptly inform the IRB and will provide the reason(s) for the termination or suspension.

Circumstances that may warrant termination include, but are not limited to:

- Determination of unexpected, significant, or unacceptable risk to mother or fetus.
- Insufficient adherence to protocol requirements.
- Data that are not sufficiently complete and/or evaluable.
- Determination of futility.

Further information regarding stopping rules can be found in the Statistical Considerations section.

